Design. This prospective, randomized, controlled trial will assess the efficacy of PE+TOP as compared to PE+PLA. Medical providers, participants, and evaluators will be blinded to the intervention condition. TOP or placebo will be administered over 16 weeks (6 weeks of upward titration and 10 weeks at maximum target dose up to 250mg per day) of active treatment, and participants will be asked to complete 12 sessions of PE during those 16 weeks (allowing for missed appointments, which are common among individuals with AUD and PTSD). Ongoing assessments of primary outcomes (i.e., heavy drinking days, PTSD symptoms, functional impairment) will be made at baseline, post-treatment, and 3- and 6-months following treatment completion. Our hypotheses are that the combined intervention (PE+TOP) will be more effective in reducing heavy drinking events and PTSD symptoms and in improving functioning and quality of life than PE with placebo (PE+PLA) among male and female Veterans with AUD and PTSD diagnoses. One hundred twenty (120) participants will be recruited through San Diego VA addictions and mental health treatment programs and randomized at the individual level. All symptomatic and interested participants who do not receive TOP during the trial will be offered the treatment immediately after blind is broken following the final assessment. In order to ensure we are examining outcomes in a multifaceted and informative manner, we will include assessments of primary comorbid conditions and multiple domains of functioning to provide the most comprehensive and informative data to inform clinical practice with this complicated population. Biweekly self-report assessment of substance use, cravings, and PTSD and depression symptoms will be completed. We will also examine differential drop out, early response, and treatment adherence.

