- **Power analysis:** We determined sample size for a two group design with PHDD as the primary outcome at post-treatment. A recent meta-analysis comparing the effects of TOP compared to placebo on heavy drinking found an overall standardized effect size of .406 [5]. The overall effect size was determined from seven studies with effect sizes ranging from .140 to .623. To ensure adequate power we calculated a sample size for a two-sample t-test by condition. The proposed primary analysis uses PHDD measured at baseline, post-intervention, 3, and 6 months in a random-intercepts regression model; however this use of additional data should serve to increase the power. A two-tailed test would require a sample size of 192 participants to detect an effect size of .406 with 80%. This is not a feasible sample size to recruit within the study's recruitment window. Alternatively, a 1-tailed test requires a sample size of 120 to have 72% power to detect the expected effect size. A one directional test is warranted given we are interested only in the improvement of PHDD for the TOP condition compared to the placebo condition. In addition, a sample size of N = 120 provides 80% power for a two-tailed test to detect a sample size of .516, a somewhat larger effect size within the range of effect sizes pooled in the recent meta-analysis [5]. Overall, we believe a sample size of N = 120 balances three needs: (1) sufficient power to compare the study groups; (2) the reality of recruiting a sample of Veterans with AUD and PTSD; and (3) overall project cost considerations.

Aims:

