- **Primary Aim Analysis.** As stated in Aim 1, we will evaluate the efficacy of PE+TOP, as compared to PE+PLA, in percent heavy drinking days (PHDD) among Veterans with comorbid AUD/PTSD at post-treatment and 3- and 6-month follow-up. The statistical model will be a generalized linear mixed model with a log link and gamma distribution variance function. If the over-dispersion parameter is close to zero a Poisson regression model will also provide equivalent model fit. The model will include a factor for treatment condition (PE+TOP, PE+PLA) and a linear term for time (baseline, post-treatment, 3, and 6 month follow-up). This model can be expanded to determine an adjusted intervention effect by including covariates such as gender and era of service. The primary test of treatment effect will be a group x time interaction. This flexible analytic method provides maximum likelihood parameter estimates based on all of the available data, allowing for the inclusion of cases with missing data and the modeling of the covariance error structure of the data across the

assessment points [90]. If the extent of missing data is small and the data appear to be consistent with a missing-at-random model, we will also carry out maximum-likelihood based on a “completer-analysis” using the observed data.

- **Secondary Aim Analyses.** As stated in Aims 2 and 3, veterans in PE+TOP, compared to PE+PLA, will show greater improvements in PTSD, depression symptoms, functional impairment and quality of life at post-treatment and 3- and 6-month follow-up. We will first examine the relationships among these outcomes to determine if composite scores should be created from highly correlated variables. This will help to reduce the number of statistical tests. The statistical model for these analyses will be random effects regression models as described in the primary aim analysis section, using identity link for Gaussian distributed linear variables and log or logit link functions for discrete or skewed outcome variables. These analyses would be in an intent-to-treat framework using maximum likelihood as before.

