Alcohol and Substance Use Measures. At baseline, participants will be administered the AUD and SUD sections of the Structured Clinical Interview for DSM-5 [SCID; 52]. The Timeline Follow-back Procedure [TLFB; 63] will be employed at all assessment points to evaluate drinking and drug use during the 90 days preceding the screening visit. The Quantity-Frequency Index [64] and maximal consumption will be calculated for alcohol use. Drug use indices will be similarly derived for other drugs. The TLFB will be used at each follow-up to establish: % heavy drinking days (HDD), % days abstinent (PDA), time to relapse to heavy drinking, length of use episodes, severity of relapse, and current alcohol/drug use pattern. The Addiction Severity Index-5th edition (ASI) interview [65] which includes seven subscales (medical, employment, alcohol use, drug use, legal, family/social, and psychiatric), will be used to assess severity of alcohol problems. A self-report Substance Use Inventory [SUI; 66] will be administered at treatment sessions. It asks on which of the preceding seven days participants used alcohol or any of seven major types of drugs. Participants will complete an initial toxicology screen at baseline and random screens will be conducted during 25% of the assessment. Relapse episodes will be classified using the Modified Contextual Cue [MCC; 67] system for precursors using transcribed verbatim reports of relapse episodes, and using Shiffman and Wills' framework of temptation, stress, or other [68]. Craving will be measured weekly using the Penn Alcohol Craving Scale [PACS; 69]. The PACS is a well validated five-item, self-report measure that includes questions about the frequency, intensity, and duration of craving, the ability to resist drinking, and asks for an overall rating of craving for alcohol for the previous week. The PTSD-specific Alcohol Expectancies Questionnaire [P-AEQ; 46] measures alcohol expectancies related to PTSD symptoms. The instrument differentiates between alcohol dependent and non-alcohol dependent

individuals with PTSD, and has good psychometric properties.

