10) Describe the characteristics of the proposed subject population. Include age, gender, ethnicity, and health status as appropriate. Provide inclusion and exclusion criteria as appropriate. Indicate the number of VASDHS participants to be studied. For multisite studies, also provide the total number of subjects from all sites. Indicate the estimated number of consented subjects that will fail the screening process, if any.

Protection of Human Subjects

1. Risks to the Subjects.

1.a. Human Subjects Involvement and Characteristics

The participants in this study will be 120 outpatient male and female Veterans (60 per treatment condition), ages 18 or older, with alcohol use disorder (AUD) and PTSD.

In order to ensure that our sample represents the diversity of comorbidity in Veterans with PTSD, exclusion criteria are minimized and include only those factors that contraindicate primary treatment for PTSD, prevent the Veteran from benefiting from the current program, or may interfere with the mechanisms under study.

Inclusion criteria are:

- 1) Veterans of the U.S. military and/or Reserve/National Guard members,
- 2) at least 18 years of age,
- 3) survivors of a psychological trauma meeting DSM-5 criterion A, and are at least one month post-trauma,
- 4) have current DSM-5 diagnoses of AUD and PTSD based on semi-structured diagnostic interviews,
- 5) have at least 20 days of heavy drinking (≥ 5 drinks/day for men and ≥ 4 drinks per day for women) in the last 90 days spent in a non-restricted environment and meet criteria for heavy drinking at least 4 days in the last 30 days prior to screening,
- 6) are not currently receiving trauma-focused psychotherapy,
- 7) are literate in English and intend to stay in the San Diego area during the study,
- 8) are willing to attend psychotherapy, medication, and assessment sessions,
- 9) trying or planning to try to cut down on or abstain from alcohol,
- 10) for females of childbearing potential, agree to use an approved form of contraception for the duration of the study, including hormonal contraceptives (e.g., oral contraceptives or implantable devices), intrauterine device (IUD), or double barrier methods (e.g., diaphragm with spermicidal condom); barrier method is preferred as topiramate may make birth control less effective,

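### The drinking calendar behind the primary outcome is tied to the 90 days before screening at every assessment, and no look-back is stated for follow-up

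*Combined protocol and SAP*

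**What the plan says.** Section 9.8 (Alcohol and Substance Use Measures) states that the TLFB "will be employed at all assessment points to evaluate drinking and drug use during the 90 days preceding the screening visit". Later in the same paragraph it adds: "The TLFB will be used at each follow-up to establish: % heavy drinking days (HDD", along with abstinent days, time to relapse and current use pattern. That sentence gives no look-back length, no anchor date and no denominator.

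The statistical part of Section 9 relies on this measure without defining its period. The power analysis says: "We determined sample size for a two group design with PHDD as the primary outcome at post-treatment". The primary aim analysis has "a linear term for time (baseline, post-treatment, 3, and 6 month follow-up", and "The primary test of treatment effect will be a group x time interaction".

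The COVID-19 procedures also list a mid-treatment assessment, which the words about all assessment points would cover.

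**The concern.** The stated rule attaches one fixed calendar period, ending at screening, to every interview. Followed to the letter, each follow-up interview would ask again about drinking before treatment. The arms could then differ in PHDD only by chance or recall, and the group-by-time test would carry no treatment signal.

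Nobody is likely to run the interview that way. Once the anchor is set aside, however, the plan offers nothing in its place. An interviewer, a programmer and a later reader could each settle on a different period for the primary outcome, and all would be consistent with the text.

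**Working it through.** **1. Is a follow-up window given anywhere else?** These are the other recall periods that might be taken for one:

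- Substance Use Inventory, Section 9.8: "It asks on which of the preceding seven days participants used alcohol or any of seven major types of drugs". It is given at treatment sessions and is not the source of PHDD.
- Penn Alcohol Craving Scale, Section 9.8: previous week, craving only.
- Inclusion criterion 5, Section 10: at least 20 heavy drinking days "in the last 90 days spent in a non-restricted environment and meet criteria for heavy drinking at least 4 days in the last 30 days". This is an entry rule.
- Constrained-environment form, Section 9.8: time since the last study visit, not linked to PHDD.

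None defines PHDD after baseline.

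**2. What the literal rule captures.** Section 9 (Design) says: "TOP or placebo will be administered over 16 weeks (6 weeks of upward titration and 10 weeks at maximum target dose". So treatment lasts 16 × 7 = 112 days, split 6 × 7 = 42 and 10 × 7 = 70. Assumptions: day 0 is the start of study drug, post-treatment is day 112, and three months is 91 days. The 3-month visit is then day 112 + 91 = 203 and the 6-month visit day 203 + 91 = 294. Screening precedes randomization, so the stated window holds 0 post-randomization days at all three visits. It would have ended at least 112, 203 and 294 days before the respective interviews.

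**3. What different intended windows would capture.** The 30- and 112-day lengths are illustrations; the protocol gives only 90 days for the TLFB.

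| Assessment | 30 days | 90 days | 112 days |
|---|---|---|---|
| Post-treatment (day 112) | 30 maintenance | 20 titration + 70 maintenance | 42 titration + 70 maintenance |
| 3 months (day 203) | 30 after treatment | 90 after treatment | 21 maintenance + 91 after treatment |
| 6 months (day 294) | 30 after treatment | 90 after treatment | 112 after treatment |

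Example: 112 − 90 = 22, so a 90-day window at post-treatment starts at day 22 and includes 42 − 22 = 20 titration days. The split by phase uses the six titration weeks in the Design paragraph. The titration paragraph instead gives weeks 1-5 for titration and weeks 6-16 for the full dose. Those passages must be reconciled, but this point does not depend on the split.

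**4. Does a common 90-day window work?** It would cover days 22-112, 113-203 and 204-294. With 91-day spacing these do not overlap; if a three-month interval ran to 89 days, the overlap would be 90 − 89 = 1 day. If mid-treatment falls near day 112 / 2 = 56 (an assumption), a 90-day look-back there would reach 90 − 56 = 34 days before the start of study drug.

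**5. Denominator.** Suppose 20 heavy drinking days are recorded in a 90-day window that includes a 28-day residential stay (the program length in the Treatment Setting paragraph). PHDD is 20/90 = 22.2% if all days count and 20/(90 − 28) = 20/62 = 32.3% if restricted days are removed. The plan does not say which applies.

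**6. The plan's sample-size figures.** Alpha is not stated; 0.05 is assumed. The two-tailed N per arm is 2(1.960 + 0.842)²/0.406² = 95.2, so 96 per arm and 192 in total, as stated (194 with the t distribution). One-tailed power with 60 per arm is Φ(0.406 × √30 − 1.645) = Φ(0.579) = 71.9%, against the stated 72%. Both rest on a standardized effect, so the window question leaves them unchanged.

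**The case against.** The strongest reply is that the intent is plain. Time to relapse and current use pattern cannot be read from a calendar that ends at screening, and the aims place heavy drinking at post-treatment, 3 and 6 months. Ninety days is the only TLFB length in the document. It matches the main entry window and roughly the spacing of the follow-up visits, so 90 days before each visit is the natural reading. This stands as evidence of intent. It does not supply the missing rule, because periods such as the days since the last assessment fit the same intent.

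Three stronger readings are tempting, and the documents do not support them.

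- **A reader might infer that the trial will measure pre-treatment drinking at follow-up.** The follow-up sentence in Section 9.8 points the other way.
- **A reader might infer a loss of power from windows that include titration days.** That requires 0.406 to be a maintenance-only effect, with no effect during titration and a standard deviation that does not change with window length. The power analysis presents 0.406 as an overall effect on heavy drinking, and the protocol's own model expects benefit early in treatment. If 0.406 described the whole treatment period instead, the same reasoning would not show that loss.
- **A reader might infer that the window can be freely chosen once the data are seen.** The interview fixes which days are recorded, so only windows inside those days could be selected later.

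**Conclusion.** Wrong as written. The stated TLFB window holds no post-randomization days at any of the three follow-up points in the primary model, and no other text defines the PHDD look-back there. The count of zero needs only that screening precedes randomization; the other day counts rest on the calendar assumptions shown above.

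The intent can be recovered in part, so this is a correction the sponsor should make rather than evidence that the design has failed. Its size is a misstated and otherwise undefined observation period for the primary outcome at three of four time points. The documents support no figure for an effect on power or bias.

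**What to change.** In Section 9.8, and again under the primary aim analysis:

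- Limit the 90 days preceding screening to the baseline TLFB.
- Define PHDD at post-treatment, 3 months and 6 months over the 90 days preceding that assessment. This keeps the only TLFB length the protocol gives, makes the window equal at all four model time points, and leaves the windows essentially non-overlapping. It is chosen for those reasons and not for power.
- Limit any mid-treatment TLFB to days since baseline, so that pre-treatment days stay out of it.
- State whether restricted-environment days count in the PHDD denominator.

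The cost is a few sentences in two places, with no change to sample size or visits. It should be settled before unblinding. If interviews have already been held, the sponsor should first confirm that the recorded days cover the 90-day windows.

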- 11) Individuals with clinically significant renal disease and/or impaired renal function, as defined by clinically significant elevation of blood urea nitrogen (BUN) or creatinine or an estimated creatinine clearance of < 60 mL/min, can be included with physician approval, however the dosing schedule and maximum dose will be adjusted in accordance with FDA prescribing guidelines,
- 12) if individual is on another addiction medication, they should be on a stable approved addiction medication dose (at least two weeks before starting study drug) throughout the study,
- 13) are capable of giving informed consent.

Exclusion criteria are:

- 1) Subjects known to have clinically significant unstable medical or psychiatric conditions, where participation is deemed by investigators and study physicians to be risky, including but not limited to:

-AST and/or ALT >5 times the upper limit of the normal range and/or an increased serum bilirubin >2 times the upper limit of normal.

-Seizure disorders

- 2) have been treated with Topiramate for any reason in the past and discontinued the drug due

to hypersensitivity reaction

3) in the opinion of the investigator, should not be enrolled because of the precautions, warnings, or contraindications listed on the Topiramate package insert, (e.g., certain types of glaucoma),

4) are pregnant, lactating, or plan to become pregnant during the period of participation in the study

5) in the judgment of the investigator, represent a significant risk of suicidal or homicidal behavior

Women and Minorities

Women comprise 11% (e.g., SAMI clinic) to 60% (Military Sexual Trauma clinic) of the Veterans seen in the clinics from which we will be recruiting, and approximately 24% of Veterans in the program are minorities. Consistent with SAMI demographics as a whole, 10% of participants in our current Merit study over the past 3 years have been women. We have been able to obtain 26% Hispanic, 16% African American, and 20% other ethnic groups, for a total of 52% from minority groups. We will continue attempts to oversample these groups to obtain adequate recruitment of females and minorities to examine effect sizes for these groups relative to male and Caucasian counterparts.

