1.b. Sources of Materials: The data relevant to the proposed project will be gathered strictly for research purposes. Blood and urine specimens obtained are for clinical and research purposes only. Sources of research data will be demographic data collected from participants recruited for this study, ratings from independent clinical evaluators, patient self-reports, toxicology screens, and through VA CPRS chart review.

Section 10.6 Verification of non-pregnancy

10.6) To include women of child bearing potential but exclude pregnant women, indicate how it will be determined that the women are not pregnant:

Women that are pregnant, lactating, or plan to become pregnant during the period of participation in the study will be excluded from participation. All eligible participants will receive a laboratory diagnostic evaluation consisting of a chemistry panel, complete blood count, liver function tests (LFTs), urine toxicology screen and pregnancy test during their screening and/or randomization appointments so that participants with any illnesses that might adversely be affected by their participation in the trial will be excluded.

Section 11 - Recruitment

11) Describe the plans for recruitment of subjects (or selection of subjects as in record review). This description must include how, when, and where potential subjects are approached as well as procedures such as data mining, physician referral, etc. Include how selection is equitable. Indicate if vulnerability to coercion may be present and if so plans to ensure voluntary participation.

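### Inclusion criterion 10 admits women on a single non-barrier contraceptive, although the same sentence warns that topiramate may weaken birth control and only prefers a barrier method

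*Combined protocol and SAP*

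**What the plan says.** Criterion 10 in Section 10 (Human Subjects) asks females of childbearing potential to use one approved form of contraception for as long as they are in the study. The accepted forms are given as "including hormonal contraceptives (e.g., oral contraceptives or implantable devices), intrauterine device (IUD), or double barrier methods". The sentence closes with the remark that "barrier method is preferred as topiramate may make birth control less effective".

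Other text that bears on pregnancy:

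- Exclusion criterion 4 bars women who "are pregnant, lactating, or plan to become pregnant during the period of participation in the study".
- Section 10.6 describes a laboratory evaluation that includes a "urine toxicology screen and pregnancy test during their screening and/or randomization appointments". Sections 9, 9.6 and 15 describe the same evaluation with the same timing.
- Section 9 (Design) states that "TOP or placebo will be administered over 16 weeks".
- Exclusion criterion 3 lets the investigator refuse enrolment on package-insert precautions. Its example is glaucoma.
- Section 15 (Risk Management) says participants will be told of the manufacturer's clinically significant warnings.
- Section 9 schedules medication appointments weekly for six weeks, then every other week to week 16.

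**The concern.** The criterion names a possible interaction between the study drug and a safeguard the trial uses. It also names the remedy, and then leaves that remedy optional. A woman whose only contraception is a pill or an implant meets criterion 10 as written, and so does a woman who uses only an IUD.

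What is at stake is pregnancy during dosing. The protocol treats pregnancy as incompatible with participation, and its general definition of a serious adverse event in Section 9.9 includes congenital anomaly. The entry test can detect a pregnancy that already exists, but it cannot prevent one that begins in week 4 or week 12. The contraceptive agreement is the main written measure aimed at that period, and it can be met by a method whose protection the protocol itself says may be reduced.

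**Working it through.** The plan states no figure to reproduce. The check is a reading of the eligibility text against the other safeguards, followed by a rough scale.

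**Step 1: who is eligible.** Criterion 10 asks for one form of contraception and joins the options with 'or'. Three kinds of user therefore qualify: hormonal alone, IUD alone, and double barrier. The closing clause states a preference, so a woman who does not follow it still qualifies.

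**Step 2: does anything else require a back-up method?**

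| Safeguard | Where | Makes a second method mandatory? |
|---|---|---|
| Exclusion for pregnancy or planned pregnancy | Section 10, exclusion 4 | No |
| Pregnancy test | Sections 9, 9.6, 10.6, 15 | No. Described at screening and/or randomization only |
| Package-insert warnings given to participants | Sections 9 and 15 | No. This informs and does not require |
| Investigator discretion on package-insert precautions | Section 10, exclusion 3 | No. Discretionary, and contraception is not mentioned |
| Medication appointments | Section 9 | No. They give physician contact, and Section 9 allows phone or telehealth |

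**Step 3: length of exposure.** 16 weeks x 7 = 112 days. Scheduled medication visits are 6 (weeks 1 to 6) plus 5 (weeks 8, 10, 12, 14 and 16), giving 11; the protocol says up to 12. No pregnancy test is described at any of them.

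**Step 4: scale.** Section 10 plans 60 participants per arm. It reports that 10% of participants in the investigators' current Merit study are women, and says of the recruiting clinics: "Women comprise 11% (e.g., SAMI clinic) to 60% (Military Sexual Trauma clinic) of the Veterans seen". Women assigned to topiramate would number:

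- at 10%: 60 x 0.10 = 6.0
- at 11%: 60 x 0.11 = 6.6
- at 60%: 60 x 0.60 = 36

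The low end is more likely, because Section 9 (Treatment Setting) places all work in the SAMI program. It is not a bound, since the protocol adds: "We will continue attempts to oversample these groups to obtain adequate recruitment of females and minorities".

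These are counts of women, not of affected women:

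affected = women on topiramate x share of childbearing potential x share relying on one non-barrier method that topiramate weakens

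The documents give neither share and no size for the interaction, so the smallest possible value is 0.

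**The case against.** The strongest reply is that the investigators saw the issue and responded to it. The interaction is stated in the criterion, contraception is required beyond the dosing period, women planning pregnancy are excluded, package-insert warnings are disclosed, and a physician sees participants often enough to act on the preference case by case. All of that is true and should be credited. None of it changes who may enrol, so the eligibility point stands.

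A second reply is that the documents give no size or dose threshold for the interaction at up to 250 mg a day, and describe no topiramate-specific fetal harm. This also stands. It limits the point to an inexpensive improvement and rules out any claim of a demonstrated hazard.

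A third reply is that a mandatory second method may deter women in a trial that keeps exclusions few. At 10% the whole trial would have about 120 x 0.10 = 12 women, so losing one or two would be noticed. That cost is real and has to be weighed.

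Three stronger readings are tempting, and the documents do not support them:

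- **Prevention during dosing depends on the entry agreement alone.** The consent pages were removed, and contraceptive instructions may be there. Their absence from the visible text is not evidence that counselling is missing.
- **Hormonal methods are the ones affected, and an IUD is safe.** The sentence speaks of birth control in general. Offering a barrier method as the remedy points to the non-barrier options, but nothing in the documents separates hormonal methods from an IUD.
- **As many as 36 women are at risk.** That figure applies one clinic's female share to the whole topiramate arm, and it counts women before either unknown share is applied.

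**Conclusion.** The point holds as a gap in an eligibility safeguard: criterion 10 admits women on a single non-barrier method while warning, in the same sentence, that the drug may make such protection less effective, and no other visible text makes a back-up method mandatory. It is worth correcting because the change is cheap and the trial excludes pregnancy.

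The size is undetermined. The affected group is probably small and may be empty. The conclusion rests on the wording of criterion 10 and on the visible sections on pregnancy and risk. It assumes nothing about which methods topiramate weakens, by how much, or what the consent form says. It has no consequence for sample size, error rates or the primary analysis.

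**What to change.** Amend criterion 10 so that the preference becomes a requirement, for example: females of childbearing potential agree to use, for the duration of the study, either double barrier methods, or a hormonal or other non-barrier method together with a barrier method; the study physician may waive the added barrier method after documenting from the FDA prescribing information that the woman's method is not affected by topiramate.

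This treats all non-barrier methods alike, as the protocol's own wording does, and leaves any exemption to the prescribing information. The form has a precedent in criterion 11, where participants with renal disease "can be included with physician approval, however the dosing schedule and maximum dose will be adjusted in accordance with FDA prescribing guidelines". Because the rule is set at entry and applies to both arms, it does not disturb the blind.

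The cost is an amendment to one criterion, with any matching consent language, and a short physician note where a waiver is used. No test or visit is added. The downside is that an occasional woman may decline the added method and not enrol, which works slightly against the aim of oversampling women.
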